5.6.2. Research Blood Samples

Research blood samples will be taken at timepoints outlined in Table 1. Refer to Appendix 4 for specific processing and handling procedures for research blood specimens. All subjects will have blood samples collected.

5.6.3. Analysis of Immunological Response

For each time point (at baseline and Weeks 7 and 13) the percent of subjects with a response will be calculated – for T-cell proliferation response, along with an exact confidence interval.

Cryopreserved Serum

Serum samples will be analyzed to evaluate molecules that may be identified and implicated in regulating anti-melanoma immune responses and/or NIVOLUMAB/ipilimumab activity such as soluble MICA, and antibodies to melanoma antigens

6. STATISTICAL PLAN

6.1. Sample Size Determination

The sample size of up to approximately 25 subjects (total of 20 including screening failures and drop-outs) is based on the study design for safety and immune assays.

6.2. Study Population

The subject populations are defined below.

6.2.1. Safety Population

The Safety Population includes all subjects in the study who received at least 1 dose or any partial dose of NIVOLUMAB and/or ipilimumab.

6.2.2. Evaluable Population

The Evaluable Population includes subjects in the Safety Population who have the correct disease diagnosis, do not have any major protocol or inclusion/exclusion violations, have no major dosing violations, and who have a valid baseline and at least one post-baseline tumor assessment.

6.3. Statistical Analysis

The data collected in this study will be analyzed by the Biostatistics group at the Perlmutter Cancer Center at NYU.

All data will be listed individually by subject. For quantitative parameters, descriptive statistics will include the mean, standard deviation, minimum, median, and maximum. For qualitative parameters, descriptive statistics will include frequency and percentage.

Unless otherwise indicated, the statistical significance will be declared if the two-sided p-value is ≤ 0.05 .

6.3.1. Demographics and Baseline Characteristics

Subject demographics and baseline characteristics including age, sex, race, height, weight, tumor information, medical conditions, etc. will be summarized using descriptive statistics

6.3.2. Concomitant Medication

Concomitant medications and significant non-drug therapies will be summarized using descriptive statistics.

6.3.3. Safety

The safety analysis will be conducted on the Safety Population. The following safety parameters will be evaluated: adverse events, clinical laboratory tests, physical examinations, vital signs, ECOG performance status, ECGs, chest radiographs, immune safety, and immunogenicity. All safety parameters will be summarized using descriptive statistics.

- **Adverse Events**

Treatment-emergent adverse events (TEAEs) are defined as signs or symptoms that emerge during treatment or within 100 days of the last dose of study drug, including those signs and symptoms that have been absent pre-treatment or that have worsened relative to the pre-treatment assessment. Any adverse event considered related to treatment will also be considered a treatment-emergent adverse event (TEAE), regardless of the elapsed time since the last dose of study drug.

An irAE, a subset of adverse events, is defined as a clinically significant adverse event of any organ that is associated with study drug exposure, of unknown etiology, and is consistent with an immune-mediated mechanism.

All adverse events recorded during the study will be summarized using descriptive statistics. The incidence of TEAEs will be summarized by body system, preferred term, verbatim of adverse event, intensity (based on CTCAE Version 4.0 grade), and relationship to each study drug (NIVOLUMAB and/or the ipilimumab).

- **Vital Signs**

The observed vital signs at each visit and the change from baseline to each post-baseline visit will be summarized by cohort using descriptive statistics.

- **Physical Examination**

Abnormal findings in physical examination will be summarized using descriptive statistics.

- **Clinical Laboratory Tests**

Clinical laboratory test values outside the normal range and clinically significant abnormal range will be flagged in the data listing.

Laboratory data will be summarized using shift tables (baseline to notable post-baseline visit). The change from baseline will be summarized using descriptive statistics.

- **ECOG**

The data observed from ECOG performance status will be summarized appropriately.

- **Other Safety Evaluations**

The results of ECGs, chest radiographs, immune safety tests, and immunogenicity will be summarized appropriately.

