i.v.	intravenous, intravenously
ICF	informed consent form
ICH	International Conference on Harmonisation
IL-2	interleukin-2
INF	Interferon
irAE	Immune-related adverse event
IRB	Institutional Review Board
irCR	Immune-related complete response
irPD	Immune-related progressive disease
irPR	Immune-related partial response

Abbreviation	Term
irRC	Immune-related Response Criteria
irSD	Immune-related stable disease
mAb	monoclonal antibody
NIVOLUMAB	PD-1-specific, fully human IgG4 mAb
MedDRA	Medical Dictionary for Regulatory Activities
mWHO	Modified World Health Organization
MPR	Mixed Lymphocyte Reaction
MTD	maximum tolerated dose
NCI	National Cancer Institute
PBMC	peripheral blood mononuclear cells
PCC	Perlmutter Cancer Center
PD-1	Programmed Death-1
PD-L1	Programmed Death-Ligand 1
PI	Propidium Iodide
PR	Partial Response
PVG	Pharmacovigilance
SAE	serious adverse event
RECIST	Response Evaluation Criteria in Solid Tumors
SOC	system/organ/class
SOP	standard operating procedure
SPD	Sum of Product Diameters
SSAE	Serious or Significant Adverse Event
TEAE	treatment-emergent adverse event
TNF	tumor necrosis factor
ULN	upper limit of normal
URTI	upper respiratory tract infection
US	United States of America
UTI	urinary tract infection
WBC	white blood cell
WHO	World Health Organization

TABLE 1: TIME AND EVENTS SCHEDULE

Examination	Screening	Cycle 1 Treatment Period ^{11, 13} (Visits must occur ± 7 days of the scheduled visit)					Cycle 2-5 Treatment Period ^{11, 13} (Visits must occur ± 7 days of scheduled visit; Every 4 weeks for 48 weeks)						Study Completion/ Early Withdrawal (Visit to occur 12 week ± week after last dose)	Survival Follow-up	
		2	3	4	5	6	7	8	9	10	11	12			
Visit	1	2	3	4	5	6	7	8	9	10	11	12			
Week	-1	1	4	7	10	12									
Timepoint (Day)	-28 to -1	1	22	43	64	78									
Research Procedures															
• Sample for immunogenicity ⁷		•			•							•	• 1 3	•	
• Serum for cytokine panel ⁷		•			•							•	• 1 3	•	
• Cellular immune assays ⁷		•			•							•	• 1 3	•	
• Cryopreserved serum ⁷		•			•							•	• 1 3	•	
• Tissue Submission ¹ 4		•	• ¹⁵	• ¹⁵	• ¹⁵	• ¹⁵	• ¹⁵	• ¹⁵	• 1 5		• ¹⁵				

Efficacy Procedures																	
CT/MRI (neck, chest, abdomen, pelvis) ^{9, 12}	•					•	•						•	•			
							1							1			
							4							4			
															•		•
CT/MRI (Brain)	•					•	•						•	•			
							1							1			
							4							4			•
Follow-up contact ¹⁰																	•
Study Drug Administration																	
Ipilimumab ¹¹		•	•	•	•												

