3.4.6 Early Discontinuation Criteria and Procedures

3.4.6.1 Discontinuation of Study Drug

It is the right and duty of the Investigator to discontinue the study drugs of any subject if he feels that discontinuation of the study drugs is necessary to protect the subject, or that there are unmanageable factors that may interfere significantly with the study procedures and/or the interpretation of results.

Administration of the study drugs will be discontinued if the subject develops a DLT, documented relapse, or other intolerability to the study drugs.

Administration of the study drugs may be discontinued during the study for any of the following reasons:

- Adverse event(s)
- Protocol violation
- Subject withdrew consent
- Lost to follow-up
- Other
- Death

For subjects who discontinue the study drugs for any reason, the remaining study visits and associated evaluations (without dosing) should be completed. Patients who discontinue the study drug(s) due to a toxicity will be followed until the toxicity resolves to baseline. Patients will continue to be followed on the protocol schedule for radiology assessments and for relapse free survival. Pharmacokinetic samples will only be collected at the visit following study drug discontinuation.

All subjects will be followed for adverse events for at least 70 days after the last dose of study drugs and for survival follow-up indefinitely until withdrawal of consent or death.

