3.4.6.2 Discontinuation from the Study

Subject participation in the study may be discontinued for any of the following reasons:

- Adverse event(s)
- Protocol violation
- Subject withdrew consent
- Lost to follow-up
- Disease relapse

-
- Death
 - Other

For subjects who discontinue the study for any reason, all evaluations associated with the Study Completion/Early Withdrawal visit should be performed. All subjects will be followed for adverse events for at least 70 days after the last dose of study drugs.

If a subject withdraws consent for study participation, every attempt will be made to determine the reason. These subjects will be asked to allow survival follow-up contacts. Subject completion status (completed versus not completed) will be documented.

For subjects who discontinue from the study without completing the Study Completion/Early Withdrawal visit, only study drug-related adverse events will be collected.

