4.6. Concomitant Therapy

All medications taken within 28 days before the administration of the first dose of any study drugs and all concomitant therapy administered during the study until 70 days after last dose of any study drug will be recorded, along with the reason for and details of therapy use.

Information on all prior and concomitant therapy for melanoma, including chemotherapies, biochemotherapies, immunotherapies, radiation, surgery, biologics, and experimental therapy will be collected.

No concomitant medication information will be collected following subject discontinuation from the study except for concomitant medication use associated with study drug-related adverse events or adverse events that lead to discontinuation from the study.

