6.8. Reporting of Serious Adverse Events and Unanticipated Problems

Following the subject’s written consent to participate in the study, all SAEs, whether related or not related to study drug, must be collected, including those thought to be associated with protocol-specified procedures. All SAEs must be collected that occur within 100 days of discontinuation of dosing. CTCAE version 4.03 terms should be used.

The collection of nonserious AE information should begin at initiation of study drug. All nonserious adverse events (not only those deemed to be treatment-related) should be collected continuously during the treatment period and for a minimum of 100 days following the last dose of study treatment. Additionally, any SAE or other AE of concern that the investigator believes may be related to study treatment and that occurs later than 30 days after last study treatment should be reported. Information for any non-serious AE that starts during the treatment period or within 70 days after last treatment will be collected from the time of the event until resolution of the event, or until the patient’s last study visit, whichever comes first. Serious adverse event information will be collected until the event is considered chronic and/or stable.

All fatal or life-threatening adverse events must be immediately reported to the Sponsor-investigator by telephone or e-mail. Within 24 hours of the event, the Serious Adverse Event (SAE) Form supplied by NYULMC must be faxed to the Sponsor-investigator and BMS, who must then inform the NYULMC IRB, PCC CTO, and DSMC within 24 hours of the event whether full information regarding the event is

known or not. Additional follow-up by the investigator will be required if complete information is not known. De-identified source documentation of all examinations, diagnostic procedures, etc. which were completed with respect to the event should be included with the SAE form. Care should be taken to ensure that the patient's identity is protected and the patient's identifiers (as assigned at the time of study enrollment) are properly mentioned on any copy of source document provided to the Sponsor-investigator. For laboratory results, include the laboratory normal ranges.

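### Adverse-event collection rules conflict (70 against 100 days after last dose, and related-only against all-cause), so the 100-day TEAE incidence may be incompletely captured

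*Combined protocol and SAP*

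**What the plan says.** Safety and tolerability is the primary objective (section 1.5), and TEAE incidence is a main summary of it.

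**Rules at 100 days**
- Section 6.3.3: a TEAE emerges during treatment or "within 100 days of the last dose of study drug". A related event counts "regardless of the elapsed time since the last dose of study drug".
- Section 6.8: non-serious events, whatever their cause, are collected for a minimum of 100 days after the last dose.
- Sections 6.8 and 6.8.2: SAEs are collected for 100 days after dosing stops. Section 6.8 states that this applies whether or not they are related.

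**Rules at 70 days**
- Section 3.4.6.1: "All subjects will be followed for adverse events for at least 70 days after the last dose of study drugs". Section 3.4.6.2 repeats this for subjects who leave the study.
- Section 6.8, same paragraph as the 100-day rule: information on a non-serious event that starts on treatment or "within 70 days after last treatment will be collected from the time of the event", up to resolution or the last study visit, whichever is earlier.
- Section 4.6: "all concomitant therapy administered during the study until 70 days after last dose of any study drug will be recorded". After a subject leaves the study, medication is recorded only for drug-related events or events that led to leaving.

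**Rule by relationship**
- Section 3.4.6.2: for subjects who leave without the completion visit, "only study drug-related adverse events will be collected".

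**Visit timing**
- Table 1, Study Completion/Early Withdrawal: "Visit to occur 12 week ± week after last dose". The size of the ± window is not legible.

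**The concern.** The window in which an event is counted and the window in which it must be recorded should be the same. Here they agree under some sections and not under others, and nothing says which section prevails. A site working from 3.4.6.1, 3.4.6.2 or the 70-day sentence of 6.8 could stop recording new non-serious events at day 70, while the analysis goes on treating the subject as observed to day 100.

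The related-only limit raises a second problem. The TEAE definition includes unrelated events, so for subjects who miss the completion visit the numerator would depend on a causality judgement made in an open-label trial. Read literally, that limit also drops unrelated SAEs in these subjects, which section 6.8 says must be collected.

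At stake is whether the TEAE incidence means the same thing for every subject. Events that are not recorded can only lower it.

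**Working it through.** The plan gives no figure to reproduce. The check sets the windows side by side and does the day arithmetic.

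**Which window governs which event**

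| Event type | Counted as TEAE (6.3.3) | Collection rules stated | Agreement |
|---|---|---|---|
| SAE, subject on study or completion visit done | to day 100 | 100 days (6.8, 6.8.2) | yes; the 70-day floors in 3.4.6.1 and 3.4.6.2 are shorter |
| Non-serious, any cause | to day 100 | 100 days (6.8) and 70 days (6.8, other sentence); floor of 70 (3.4.6.1, 3.4.6.2) | no |
| Related, any | no time limit | related SAEs or events of concern reportable after day 30 with no stated end (6.8) | broadly yes |
| Unrelated, subject left without completion visit | to day 100 | not collected (3.4.6.2); collected (6.8) | no |

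**Length of the mismatch**
- 100 − 70 = 30 days (days 71-100), and 30/100 = 30% of the post-dose TEAE window.
- Completion visit: 12 × 7 = day 84. Then 100 − 84 = 16 days of the window remain after it.
- If the illegible window is ±1 week (an assumption), the visit falls on days 77-91, which leaves 100 − 91 = 9 to 100 − 77 = 23 days.
- The follow-up contact described in the Table 1 footnotes records survival, later treatment and progression. Adverse events are not listed there.

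**Weight of one event**
- One subject is 1/20 = 5 percentage points, or 1/25 = 4 points if all 25 are treated. This applies only when the missed event is that subject's first under the term being tabulated.

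**Illustration only.** The documents give no rate of late unrelated non-serious events. Suppose a proportion p of subjects has a new one in days 71-100. The expected number is n × p, and the chance of at least one is 1 − (1 − p)^n.

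| p (assumed) | n = 20: expected; chance of ≥ 1 | n = 25: expected; chance of ≥ 1 |
|---|---|---|
| 2% | 0.4; 33% | 0.5; 40% |
| 5% | 1.0; 64% | 1.25; 72% |
| 10% | 2.0; 88% | 2.5; 93% |

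These are numbers exposed to the conflict. They are not numbers that would in fact be missed.

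**The case against.** The strongest reply is that the plan already contains the right rule. Section 6.8 requires all non-serious events for at least 100 days regardless of relationship, and SAEs are at 100 days in both places. The 70 days in 3.4.6.1 and 3.4.6.2 is a floor that a 100-day practice satisfies, and a site that stopped at day 70 would breach 6.8. The 70-day sentence in 6.8 can be read as saying how long an event is followed rather than which events are captured. Section 5.1.5 also says that events are collected throughout the study. All of this stands, and it rules out saying that the plan as a whole permits stopping at day 70. It does not settle which rule prevails. Even on the follow-up reading, that sentence leaves events starting on days 71-100 without a follow-up rule of their own.

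A reader might also infer that delayed immune-related events are what would be lost. The documents do not support that. Such events are by definition associated with study drug. Related events count without time limit, related SAEs and events of concern remain reportable, and section 6.11 puts drug-related events of Grade 2 or above and irAEs of Grade 3 or above on expedited notification.

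Nor do the documents show that subjects who stop for toxicity are collected most narrowly. Those who only stop drug complete the remaining visits, and their toxicity is followed until it returns to baseline (3.4.6.1). The related-only limit applies only to those who leave the study and miss a visit that 3.4.6.2 says should be done. Section 2.2 also provides for exams after treatment, at which earlier events could come to light, although it does not say that events are collected there. Finally, the 70-day limit on concomitant therapy does not change TEAE counts. It affects only the record of treatment given for late events.

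**Conclusion.** The concern holds as an internal contradiction in the collection rules, not as proof that late events are under-collected. Two groups of events are exposed: unrelated or minor non-serious events starting on days 71-100, and unrelated events of any seriousness in subjects who leave without the completion visit. If the 70-day or related-only rules were followed as written, the 100-day TEAE incidence would be biased downward. The size cannot be given, because the documents state neither a late-event rate nor an expected number of subjects who miss the visit.

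The 30-day mismatch follows directly from the text. The 16-day interval after the completion visit rests on the 12-week figure in Table 1, and the 9-23 day range rests on an assumed ±1 week. The safety rows of Table 1 are not in the text available, so nothing is inferred from their absence. The DLT definition (29 days after first dose) and the DLT stopping rule are not affected.

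**What to change.** - Use the 100-day window of the TEAE definition in 3.4.6.1, 3.4.6.2, 4.6 and both sentences of 6.8 on non-serious events. In 6.8, make sure that ending collection at the last study visit cannot cut it off before day 100.
- In 3.4.6.2, replace the limit to drug-related events with collection of all adverse events to day 100 unless the subject withdraws consent to it.
- Optionally, ascertain events to day 100 by one telephone contact per subject, or ask about them at the next scheduled follow-up contact. Aligning the wording does not by itself provide a contact after about day 84.

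The cost is a wording amendment, up to 30 more days of adverse-event and medication recording per subject and, if the option is taken, one call. Treatment, visits on treatment, sample size and the stopping rules do not change.

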6.3.4. Immunology Parameters

The data from each of the assays and assessments described in Appendix 4 will be summarized by week of study, using standard descriptive statistical methods – preferably parametric if the distribution of the continuous assay data (possibly after transformation) is compatible with the assumptions of a normal distribution, and non-parametric otherwise. For each immunological marker studied, one of the following 4 transformations will be used: identity (ie, no transformation), square-root, cube root, or log transformation. Choice of the transformation will be made by computing the Anderson-Darling statistic based on the regression model residues using the pooled data. Then the transformation with the lowest Anderson-Darling statistic will be selected as the most normal-like and used in the mixed model analysis.

Scatterplots of the data for the individual subjects, over time, will be constructed to display the patterns; means (or geometric means or medians) with confidence intervals will also be plotted; contingency tables will be used for the categorical assay responses. For baseline and weeks 7 and 13, regression methods (linear or logistic) that accommodate random effects will be used to evaluate the effect of the treatment regimen on the overall levels and on the trends over time – with subject as the random effect and week as the fixed effects. These analyses will be used to evaluate the quantitative effects of the NIVOLUMAB + ipilimumab regimen on immunologic and pharmacodynamic changes due to treatment. While formally proving that the addition of NIVOLUMAB to ipilimumab will increase the probability of clinical benefit is beyond the scope of this trial, the data obtained will be used to test the hypothesis that the magnitude of the proliferating T-cells (as continuous) will increase with NIVOLUMAB added to ipilimumab compared to the prior cohorts of protocol 15651 at Moffitt Cancer Center with NIVOLUMAB alone. Note that the pre and post treatment assays from any given subject that are used in the analysis are always performed on the same plate, thus eliminating a potential confounding factor due to plate-to-plate assay variation.

Due to the exploratory nature of this trial, there will be no formal adjustments made to account for the multiple statistical testing performed on the 11 surface and intracellular biomarkers under investigation. However, to guard against having a possibly over-inflated overall type I error rate, result sensitivity will be high if 3 or more phenotypic changes occur with addition of ipilimumab at an individual α level of 0.05 each for further studying these phenotypic changes in NIVOLUMAB + ipilimumab treated cells. In the case of doing 11 independent hypothesis testings with an α level of 0.05 each, the probability of having 3 or more significant results by chance will be only about 0.015, whereas, the probability of having at least 1 or 2 significant results is 0.43 or 0.10, respectively

In addition to analyzing the results of these assays as continuous variables, the T-cell proliferation assay results will be classified as “response” or “non-response” to further explore the relationship of immunologic changes with treatment.

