6.3.4.1. T-cell Proliferation

The definition of augmented proliferation for the purposes of this trial will be a 20% increase, at Week 12, in the absolute proportion of CD107a positive CD8+ T cells that stain with the Ki-67 marker.

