Appendix 4: Description of Use of Blood Samples for Immune Analyses

Detection of Proliferating T cells After NIVOLUMAB + ipilimumab Treatment

Two different but complementary methods (Ki-67 and propidium iodide staining) will be used to detect proliferation of T cells in the peripheral blood of subjects on this trial. Pre-treatment (pheresis), and on weeks 5 and 9 (80 mL sample of blood in green top heparinized tubes on infusion days, prior to infusion) and week 12 follow-up (pheresis) during the trial, PBMC cells will be stained with PI, anti-CD3, anti-CD4, anti-CD8 (T cell markers) and anti-CD56 (NK marker). PI staining will define the proportion of cells in S-phase, and Ki-67 staining with anti-CD3/4/8/56 will define the proliferating compartment. Although it is felt that the proportion of proliferating Ki-67(+) cells and the proportion of cells in S phase will be identical (77), Ki-67 staining will be the “gold” standard to define the proliferating population in case the two parameters are in disagreement. A value of 1.0 % Ki-67 staining will be regarded as minimal evidence for proliferation in subjects based on data from HIV subjects (77). In a recent study in HIV infected subjects, Ki-67 staining was found to correlate closely ($r=0.90$) with an in vivo detection technique for T cell proliferation using deuterated glucose to label the DNA sugar backbone (78). Fresh PBMC will be stained with anti-CD3-PerCP, anti-CD4-APC and anti-CD8-PE (all from Becton-Dickinson). After washing, cells will be lysed at room temperature for 40 minutes, and stained with anti-Ki-67 (MIB-1 from B-D) in PBS with 0.5% NP-40 and 5% FCS at room temperature for 45 minutes. Cells will be washed and fixed with 1% paraformaldehyde and run directly using a FACScan flow cytometer (Beckman-Coulter). All tests will be batched and run simultaneously. The definition of augmented proliferation for the purposes of this trial will be a 20% increase in the absolute proportion of antigen-specific, tetramer positive CD8+ T cells that stain with the Ki-67 marker. We will also assess the phenotype of circulating CD8 and CD4+ T cells in this study using antibodies against markers including HLA-DR, CD25, CD44, CD45 RO/RA, CD62L, CD73, CD95, CD127, FOXP3, PD-1, CTLA-4, BTLA, CD160, Tim3, LAG3, VISTA, 41-BB, OX-40, and ICOS.

Polymorphism Analysis

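### T-cell response is ruled by a 20% increase, yet it is to be tabulated, and in the logistic option modelled, at baseline, where nobody can be a responder

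*Combined protocol and SAP*

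**What the plan says.** Four places in the protocol bear on this.

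- **6.3.4 Immunology Parameters, classification.** Besides the continuous analysis, "the T-cell proliferation assay results will be classified as" response or non-response. No other assay is dichotomised by name.
- **6.3.4.1 T-cell Proliferation and Appendix 4, the rule.** Section 6.3.4.1 defines augmented proliferation as "a 20% increase, at Week 12, in the absolute proportion of CD107a positive CD8+ T cells that stain with the Ki-67 marker". Appendix 4 has "a 20% increase in the absolute proportion of antigen-specific, tetramer positive CD8+ T cells that stain with the Ki-67 marker", a different cell population and no week. Neither states the reference value, or whether 20% is relative or in percentage points.
- **5.6.3 Analysis of Immunological Response, the table.** "For each time point (at baseline and Weeks 7 and 13) the percent of subjects with a response will be calculated", for T-cell proliferation, with an exact confidence interval.
- **6.3.4, the model.** "For baseline and weeks 7 and 13, regression methods (linear or logistic) that accommodate random effects will be used", "with subject as the random effect and week as the fixed effects". Whether week is a factor or numeric is not stated.

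Appendix 4 also gives a level: "A value of 1.0 % Ki-67 staining will be regarded as minimal evidence for proliferation". It is not called a response.

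**The concern.** An increase needs an earlier value to increase from, and the only pre-treatment value is baseline. At baseline itself no subject can have increased, so the first row of the 5.6.3 table is zero whatever the treatment does. If the same binary variable enters the logistic option of 6.3.4 with baseline as a time point, the week effect of most interest is measured against that structural zero.

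Immune response at Week 12 is a secondary objective (1.6). A reader of the results could take a step from 0% at baseline to some positive percentage later as evidence of a treatment effect, although part or all of that step comes from the definition.

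**Working it through.** The plan gives no expected response rate, assay variability or power for this endpoint, so there is no figure of its own to reproduce.

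**Inputs.** n = 20 planned, up to 25 enrolled (Synopsis). Time points baseline, Week 7 and Week 13 (5.6.3, 6.3.4). Assay CV: not given, assumed over a range.

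**1. Baseline row.** The exact 95% upper limit for 0/n is 1 − 0.025^(1/n).
- n = 20: 1 − 0.025^(1/20) = 0.168
- n = 25: 1 − 0.025^(1/25) = 0.137

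These limits quantify sampling uncertainty about a rate that is fixed at zero, so they tell the reader nothing.

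**2. Logistic model, week as a factor.** With random intercept u and baseline logit b0, each subject contributes 1 / (1 + exp(b0 + u)) at baseline, the probability of no response. This grows towards 1 as b0 falls, whatever the other parameters are. The likelihood therefore has no maximum at a finite b0.

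Invented example, n = 20: 4 respond at both later visits, 2 at Week 7 only, 4 at Week 13 only, 10 at neither (6/20 and 8/20). Maximised log-likelihood for a fixed baseline logit, by numerical quadrature:

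| Baseline logit | Log-likelihood |
|---|---|
| −2 | −28.099 |
| −5 | −24.856 |
| −10 | −24.418 |
| −20 | −24.412 |
| −40 | −24.412 |

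The ceiling is the fit to the two later visits alone: 4 ln 0.2 + 2 ln 0.1 + 4 ln 0.2 + 10 ln 0.5 = −24.412. It is approached only as b0 goes to minus infinity, so contrasts of Week 7 or Week 13 with baseline have no finite estimate.

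Week 13 against Week 7 does not use the baseline row. Here it is ln(4/2) = 0.69 logits. It is finite because subjects switch in both directions; were that not so, the cause would be the later data and not the baseline zeros.

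**3. Logistic model, week numeric (0, 7, 13).** The same data give a finite slope of 0.29 logits per week. The later visits alone give 0.69 / 6 = 0.12. The difference comes from the structural zeros.

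**4. Noise, illustration only.** Suppose there is no treatment effect, within-subject noise is log-normal, and 20% is relative. Then P(response) = 1 − Φ(ln 1.2 / (σ√2)), with σ² = ln(1 + CV²).

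| Assumed CV | σ | P(rise of 20% or more) | Expected in 20 |
|---|---|---|---|
| 5% | 0.050 | 0.005 | 0.1 |
| 10% | 0.100 | 0.098 | 2.0 |
| 15% | 0.149 | 0.194 | 3.9 |
| 20% | 0.198 | 0.258 | 5.2 |
| 30% | 0.294 | 0.330 | 6.6 |

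If 20 percentage points is meant, simulation gives at most 0.003 for a baseline Ki-67 of up to 10%, even at CV 40%, and 0.048 at a baseline of 20% with CV 40%.

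**5. Continuous alternative.** A paired t test on log values, with n = 20 and no effect, had simulated type I error of 0.050 to 0.052 for CV 10 to 30%. The continuous route does not share the defect.

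**The case against.** The strongest reply is that the protocol never says the increase is from baseline and never links response to augmented proliferation. A percentage planned at baseline fits a level rule, such as the 1.0% Ki-67 level in Appendix 4, better than a change rule. This stands in part: the link is a strong inference, not stated text. But the 1.0% level is called minimal evidence for proliferation, and if it was the intended rule, the plan has to say so. As written, either the baseline rate is empty or the response rule is missing.

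Three stronger readings are tempting, and the documents do not support them.

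- *The week effect cannot be estimated.* The modelling sentence covers linear as well as logistic regression, and most of 6.3.4 concerns continuous data. The failure is confined to contrasts of the binary response with baseline when week is a factor.
- *Noise will give a false significant result.* One can set later responders against the baseline zero in an exact McNemar test: 6 of 20 gives p = 2 × 0.5^6 = 0.031, and noise alone would reach that with probability 0.010 to 0.693 at CV 10 to 30%. No such test is planned: 5.6.3 asks for a percentage and interval, and the Synopsis calls the immune summary descriptive. The figures also need an assumed CV and the relative reading of 20%.
- *The plan lacks a sound analysis of proliferation.* It has one, the continuous mixed model with subject as random effect; the binary version is added for exploration.

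Section 6.3.4 also puts a subject's pre- and post-treatment assays on the same plate. That removes plate-to-plate variation, but not within-plate or day-to-day biological variation.

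**Conclusion.** The point holds for the binary T-cell response only. Followed as written, the baseline percentage is 0/n by construction, and logistic contrasts with baseline have no finite estimate when week is a factor. With week numeric, the slope is pulled by the structural zeros. Any comparison of the response rate with baseline can point only one way. This rests on reading response as the 20% increase and its reference as baseline.

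The share of subjects who would respond through noise is unknown: about 10 to 33% under a relative reading and an assumed CV of 10 to 30%, and close to nil under a percentage-point reading at low baseline Ki-67. That spread is itself a reason to state the scale. The continuous model, Week 13 against Week 7 and the primary safety objective are unaffected. The correction is worth making because it is cheap and concerns a secondary objective.

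**What to change.** - In 5.6.3 and 6.3.4, calculate the change-based response and its exact interval at post-baseline visits only, and exclude baseline from any logistic model of it.
- State that the treatment effect on proliferation is judged from the already planned continuous mixed model of Ki-67, with baseline included, and that the binary response is descriptive.
- State the reference value (baseline) and the scale (relative or percentage points). Reconcile the rule, which 6.3.4.1 ties to Week 12, with the Weeks 7 and 13 used in the analysis; Appendix 4 samples at weeks 5, 9 and 12. Reconcile the two cell populations as well.
- If a noise reference is reported on the relative scale, use the mirror-image decrease: a ratio of 1/1.2 = 0.833 or less, a fall of about 16.7%. A 20% fall would understate noise (5.7% against 9.8% for a 20% rise at CV 10%). Note that a true treatment effect would also reduce the mirror-image rate.
- If the 1.0% Ki-67 level was the intended response rule, name it as such; tabulation at baseline is then valid.

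The cost is a wording change with no new data. The one loss is that no p-value is given for the response percentage against baseline.
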